9.6.2 Pharmacogenetics Confidentiality

All pharmacogenetic samples and the information associated with the samples will be coded and stored appropriately to ensure confidentiality of the patient's information and to enable destruction of the samples if requested. Since the evaluations are not expected to benefit the patient directly or to alter the treatment course, the results will not be placed in the patient's medical record and will not be made available to members of the family, the personal physician, or other third parties, except as specified in the informed consent.

9.7 Data collection and documentation

It is the Investigator's responsibility to ensure that all relevant data is clearly recorded in the medical records. The Investigator must allow the RM-CTU direct access to relevant source documentation for verification of data entered into the CRF, taking into account data protection regulations. The clinical data should be recorded in the CRF and the following must be verifiable by the source data: patient consent, medical history, patients eligibility for participation in the trial, study treatment administration (pembrolizumab and radiotherapy), routine haematology and biochemistry and response to treatment.

The patients' medical records, and other relevant data, may also be reviewed by appropriate qualified personnel independent from the sponsor appointed to audit the trial, or by REC. Details will remain confidential and patients' names will not be recorded outside the hospital.

The Principal Investigators at each centre are confirming agreement with his/her local NHS Trust to ensure that

- sufficient data is recorded for all participating patients to enable accurate linkage between hospital records and CRFs
- source data and all trial related documentation are accurate, complete, maintained and accessible for monitoring and audit visits
- original consent forms are dated and signed by both patient and investigator and are kept together in a central log together with a copy of the specific patient information sheet(s) given at the time of consent
- all essential documents must be retained after the trial ends to comply with current legislation

No study document will be destroyed without prior written agreement between the Sponsor and the PI. Should the PI wish to assign the study records to another party or move them to another location, written agreement must be obtained from the Sponsor.

9.8 End of Trial

The end of the trial is defined as the last patient's last visit.

10.0 DATA AND STUDY MANAGEMENT

10.1 Source Data

All information in original records and certified copies of original records of clinical findings, observations, or other activities in a clinical trial necessary for the reconstruction and evaluation of the trial are classified as source data. Source data are contained in source documents; these are defined as original documents, data, and records e.g., hospital records, clinical and office charts, laboratory notes, memoranda, patients' diaries or evaluation checklists, pharmacy dispensing records, recorded data from automated instruments, copies or transcriptions certified after verification as being accurate copies, microfiches, photographic negatives, microfilm or magnetic media, x-rays, patient files, and records kept at the pharmacy, at the laboratories and at medico-technical departments involved in the clinical trial.

10.2 Language

All CRFs will be in English. Generic names for concomitant medications should be recorded in the CRF wherever possible. All written material to be used by patients must use vocabulary that is clearly understood, and be in the language appropriate for the study site.

10.3 Data Collection

The medical records/medical notes should be clearly marked and allow easy identification of a patient's participation in the clinical trial. The Investigator (or delegated member of the site study team) must record all data relating to protocol procedures, IMP administration, laboratory data, safety data and efficacy data into the CRF.

10.4 Recording of Data

Patients' data will be documented on a trial specific CRF designed by RM-CTU. Upon signing the informed consent form, the patient is assigned to the next sequential trial identification number and reviewed for eligibility.

The Investigator is responsible for ensuring the accuracy, completeness, clarity and timeliness of the data reported in the CRFs. Only the Investigator, and those personnel who have completed the Study Team Responsibilities Signature Log/Delegation Log as authorised by the PI, should enter or change data in the CRFs. All protocol required investigations must be reported in the CRF. The Investigators must retain all original reports, traces and images from these investigations for future reference. The data will be entered in a clinical trials database (Macro V4). If a patient withdraws from the study, the reason must be noted on the CRF.

The CRF will be signed by the Investigator or by an authorised staff member. Study specific information will be entered into an CRF visit by visit. Data that are derived should be consistent with the source documents or the

discrepancies should be explained. All CRF data should be anonymous, *i.e.* identified by study patient number only.

Once the patient is 'off study' and the CRF has been fully completed, the Investigator must provide a signature to authorise the complete patient data.

10.5 Data Management

Data management will be carried out by RM-CTU using an electronic database and in accordance with the data management plan agreed by the RM-CTU and RDSU. Data entry will be carried out by appropriately trained personnel at participating centres. Queries will be raised centrally by the trial manager / trial monitor and sent to the participating centre for resolution.

10.6 Study Management Structure

10.6.1 Delegations of Responsibilities

This trial is co-sponsored by the Royal Marsden NHS Foundation Trust and The Institute of Cancer Research. This trial will be conducted in accordance with the professional regulatory standards required for non-commercial research in the NHS under the research governance framework for health and social care and good clinical practice. The following responsibilities have been delegated to:

10.6.1.1 RM-CTU

RM-CTU has overall responsibility for facilitating and coordinating the conduct of the trial and is also responsible for collating data obtained, and undertaking and reporting all analyses.

The responsibilities of RM-CTU for the day-to-day management of the trial will include the following.

- ensuring an appropriate ethics opinion has been sought, and any amendments have been approved
- giving notice of amendments to protocol, make representations about amendments to the Main REC and MHRA as applicable
- notifying sites and Sponsor that the trial has ended
- randomising patients
- raising and resolving queries with local investigators
- keeping records of all serious adverse events (SAEs), overdose incidents, pregnancies and overdose and liver toxicity ECI's reported by investigators
- notifying the Main REC, MHRA and Investigators of related Serious Adverse Events

10.6.1.2 MSD

- Provision of pembrolizumab

10.6.1.3 Participating Sites

- putting and keeping in place arrangements to adhere to the principles of GCP
- keeping a copy of all 'essential documents' (as defined under the principles of GCP) and ensuring appropriate archiving of documentation once the trial has ended
- taking appropriate urgent safety measures
- .

10.7 Protocol compliance and amendments

All participating sites will be required to sign and adhere to the trial protocol.

Any protocol amendment should be agreed with the trial management group (TMG) and be approved by the sponsor prior to submission and review by the relevant Ethics Committee. Once favourable opinion from EC has been obtained the amendment can be distributed to sites and implemented. It is the responsibility of the Principal Investigator to submit amendment to their R&D department for R&D approval.

10.8 Trial Management

The RM-CTU will be responsible for the day-to-day coordination and management of the trial. This includes all duties relating to safety reporting. If applicable a trial agreement will be signed between the site and RM-CTU. Once all relevant trial approvals are in place an initiation (visit or teleconference) will be conducted. In addition, training and ongoing advice will be provided by trial training workshop(s), site initiation and ongoing site support to each participating site by Trial Management Group (TMG).

10.8.1 Trial Management Group (1 per study)

A Trial Management Group (TMG) will be set up and membership will include Chief Investigator, Co-Investigators, Trial Statistician and Trial Manager. Principal Investigators and other key study personnel will be invited to join the TMG as appropriate. The TMG has operational responsibility for the conduct of the trial. The TMG is bound to act on the advice of the Pembrolizumab Project Safety Review Committee (PPSRC) but is also responsible for monitoring recruitment, safety and governance of the trial as well as collaborating with subsequent translational sub-studies. The TMG will also review any safety concerns and can convene a meeting of the PPSRC if significant concerns exist.

10.8.2 Pembrolizumab Project Safety Review Committee (PPSRC)

PPSRC has been established to coordinate the management and governance of 4 phase 1 trials evaluating Pembrolizumab in combination with standard of care radiotherapy in different tumour types (bladder, cervix, head and neck, or lung). The PPSRC will include the chief investigators of all 4 Pembrolizumab trials ([name], Confidential

[name], [name] and [name]), Representative from RM-Clinical Trials Unit, Senior Statistician and be chaired by [name],. The PPSRC will meet monthly and at every dose escalation point, the meeting frequency maybe decreased during the expansion phases of all the studies if considered safe to do so. The role of the PPSRC is:

- Review relevant safety data and make dose escalation decisions for all studies
- Reviews all SAEs and emerging safety data both from RM Sponsored studies and external SUSARS received from MSD
- Monitor progress of the trials and ensure emerging safety information is evaluated and protocol and GCP principles are adhered to.

The PPSRC terms of reference, roles and responsibilities will be defined in a charter. Further internal or external experts may be consulted as necessary.

10.9 Monitoring

During the trial RM-CTU is responsible for monitoring data quality in accordance with relevant standard operating procedures (SOPs). Incoming data will be monitored for protocol compliance and if any inconsistent or missing data is identified queries will be sent to the site for resolution. Any systematic inconsistencies may trigger an onsite monitoring visit.

The trial statistician will periodically examine the data for anomalies and outliers, such as too few or too many events. Queries will be raised by the trial coordinators in such situations and communication with the clinical teams will take place. In addition statistical monitoring of unusual dates and inconsistent data will take place (for example clinic visits on Sundays). Again these will raise queries via the trial coordinators.

If an on-site monitoring visit is required, RM-CTU will contact the site to agree convenient date. The site must ensure that relevant site file and patient notes are available for review. RM-CTU staff conducting onsite monitoring will review the investigator site file and carry out source data verification to confirm compliance with the protocol, trial agreement.

10.10 Quality Control and Quality Assurance

Quality Control (QC) will be performed according to RM-CTU internal procedures. The study may be audited by a Quality Assurance (QA) representative of the Sponsor. All necessary data and documents will be made available for inspection.

10.11 Clinical study report

Clinical data will be presented at the end of the trial based on final data listings. The CI,/designee together with the trial statistician will prepare a brief clinical study report / publication based on the final data listings. A summary of the report must be provided to the Research Ethics Committee.

10.12 Record retention

Essential documents are documents that individually and collectively permit evaluation of the conduct of the trial and substantiate the quality of the data collected. During the clinical trial and after trial closure the Investigator must maintain adequate and accurate records to enable both the conduct of a clinical trial and the quality of the data produced to be evaluated and verified in accordance with current legislation.

The Chief investigator will maintain essential documents to facilitate the management of the trial, audit and inspection in accordance with RM G-SOPs and in compliance with the clinical trial regulatory requirements.

The medical files of trial subjects shall be retained in accordance with national legislation and in accordance with the maximum period of time permitted by the hospital, institution or private practice. All medical records and TMF documentation will be retained for a minimum of 15 years after the study has concluded.

10.13 Reporting and publication

The trial results will be submitted for publication in a relevant medical journal with authorship according to the criteria defined by the ICMJE (<http://www.icmje.org>). These state that: Authorship credit should be based 1) substantial contributions to conception and design, acquisition of data, or analysis and interpretation of data; 2) drafting the article or revising it critically for important intellectual content; and 3) final approval of the version to be published. Authors should meet conditions 1, 2, and 3.

Draft publications (manuscripts, abstracts, slides and posters) should be circulated to the relevant parties to allow sufficient time for review prior to submission. There will be a fifteen (15) day period to review abstracts or posters and a thirty (30) day period to review slides and manuscripts and respond to the author with any revisions.

12.0 APPENDICES

12.1 Appendix 1: Dose-Modification Guidelines for Chemotherapy

Toxicities are to be assessed according to the CTCAE version 4.0. Patients should be monitored closely for toxicities, and the cisplatin dosing should be withheld or reduced according to degrees of toxicity.

The guiding principle for dose modifications in patients receiving therapy with MK-3475, cisplatin, and radiotherapy is to modify only the treatment responsible for the toxicity in question, if the toxicity is entirely consistent with 1 of the 3 treatments. Therapy with the other treatment may continue while treatment with the presumptive causative agent is interrupted or modified. In contrast, if the toxicity in question cannot be easily attributed to 1 of 3 treatments, then further treatment with each of the agents may need to be discontinued, interrupted, or modified. Treatment modifications will, however, take into account that radiation therapy is the foundation therapy being employed, and adjustments to the radiotherapy regimen will only be made if unavoidable due to the toxicity observed.

12.1.1 Dose Limiting Toxicity for Cisplatin

12.1.1.1 Haematological Toxicity

Hematologic Toxicity	Cisplatin Modifications of Dose and Regimen
ANC < 1200/mm ³	Withhold cisplatin therapy until toxicity resolves. When toxicity resolves (ANC > 1200) reinitiate cisplatin at same dose.
Neutropenic fever	Permanently reduce cisplatin dose by 25%.
Platelet count is < 75,000 /mm ³	Withhold cisplatin therapy until toxicity resolves. When toxicity resolves (> 75,000 per cu. mm) reinitiate cisplatin at

	same dose.
Thrombocytopenia with bleeding	Permanently reduce cisplatin dose by 25%.

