Treatment / Main Study Procedures	
Patients will be registered to receive pembrolizumab in combination with platin-based chemoradiotherapy. A pre-loading dose of 100 or 200mg (dependent on dosing level) of pembrolizumab will be given once the patient has completed the screening period. Patients will then return 2 weeks later to begin cycle 1 of a regimen of pembrolizumab 3 weekly at a dose of 100 or 200mg (dependent on dosing level) for a total of 7 cycles (3 during chemoradiotherapy and 4 after chemoradiotherapy).
 
Clinical assessments will be undertaken at the pre-loading dose and then every 3 weeks on the day on which the drug is administered. Patients will continue on this regimen until they complete all 8 doses of pembrolizumab, suffer disease progression, unacceptable toxicities, discontinue the study medication for any other reason or withdraw from the study. Chemoradiotherapy will begin with the cycle 1 dose of pembrolizumab and will continue for 35 fractions over a period of 7 weeks.
 
After the last dose of pembrolizumab patients will be expected to attend post-treatment follow-up visits as described below and/or safety follow-up (SFU) at 12 weeks or earlier if initiating a new anti-cancer treatment. Follow up requirements for patients are as follows:
 
 • If a patient completes all 8 doses of pembrolizumab without disease progression or unacceptable toxicities they will be seen at 4 weeks and 8 weeks after the last dose of pembrolizumab for the post treatment follow up. They will then return at 12 weeks for the SFU and after this be followed up every 4 weeks for 9 months to assess for disease status and the initiation of a new anti-cancer treatment. If the patient progresses or begins a new treatment during this time then they will move into the survival follow up every 12 weeks by telephone for overall survival until death, withdrawal of consent, or the end of the study • If a patient discontinues for reasons other than disease progression they will be seen at 8 weeks after the last dose of pembrolizumab for the post treatment follow up. They will then return at 12 weeks for the SFU and after this be followed up every 8 weeks for 9 months to assess disease status until progression, initiating a non-study cancer treatment or withdrawal. If a patient progresses or begins a new anticancer therapy patients will be followed every 12 weeks by telephone for overall survival until death, withdrawal of consent, or the end of the study. • If a patient progresses at any time in the study they would be expected to complete a SFU visit at 12 weeks after their last dose of pembrolizumab or before the initiation of a new anti-cancer treatment, whichever comes first. They will then move into survival follow up and will be followed every 12 weeks by telephone for overall survival until death, withdrawal of consent, or the end of the study. 
Patients will also undergo tumour assessment by RECIST 1.1 at screening, 8 weeks post chemoradiotherapy (cycle6) and then every 12 weeks for 12 months (irrespective of delays

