that there was no significant impact of tumor burden on exposure. In addition, exposure was similar between the NSCLC and melanoma indications. Therefore, there are no anticipated changes in exposure between different indication settings.

It has therefore been decided to use a dosage of pembrolizumab that will be based on a total dose and not defined by weight. This will be either 100 mg (dose level 1) or 200 mg (dose level 2). The decision to include dose level 1 (100 mg q 3 weeks) is based on the fact that this therapeutic combination has never been tested in patients with newly diagnosed LA-SCCHN who are receiving curative chemoradiotherapy. In such patients, any interruptions or delays to chemoradiotherapy can have a negative impact on treatment outcomes. For this reason, we have chosen to be cautious in treating an initial cohort at 100 mg q 3 weeks – rather than the usual single-agent dose of 200 mg q 3 weeks.

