2. For patients that have discontinued treatment for any reason other than progression and have not withdrawn consent for participation.

3. Or before the initiation of a new anti-cancer therapy whichever comes first.

4. Only applicable if patients come off between on treatment visit cycles.

5. Where feasible and if the patient has consented OPTIONAL post-treatment research tumour biopsies will be taken at week 0 and week 3.

6. In patients with N+ Disease.

7. CT / MRI Imaging should be completed at screening, Week 15 (Cycle 6) and then every 12 weeks for 12 months or until disease progression, discontinuation or initiation of another anti-cancer treatment.

8. C3 Wk 7 is not a clinic visit. Patient will continue to receive radiotherapy only.

Table 2: Schedule of Study Assessment

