6.5 Rescue Medications & Supportive Care

6.5.1 Supportive Care Guidelines

Patients should receive appropriate supportive care measures as deemed necessary by the treating investigator including but not limited to the items outlined below:

6.5.1.1 Diarrhoea:

Patients should be carefully monitored for signs and symptoms of:

- Enterocolitis (diarrhoea, abdominal pain, blood or mucus in stool, with or without fever)
- Bowel perforation (peritoneal signs and ileus).

In symptomatic patients, infectious etiologies should be ruled out, and if symptoms are persistent and/or severe, endoscopic evaluation should be considered.

- In patients with severe enterocolitis (Grade 3):
 - Pembrolizumab will be **permanently discontinued** and treatment with systemic corticosteroids should be initiated at a dose of 1 to 2 mg/kg/day of prednisone or equivalent. When symptoms improve to Grade 1 or less, corticosteroid taper should be started and continued over at least 1 month.
- In patients with moderate enterocolitis (Grade 2):
 - Pembrolizumab should be **withheld** and anti-diarrhoeal treatment should be started. If symptoms are persistent for more than one week, systemic corticosteroids should be initiated (e.g., 0.5 mg/kg/day of prednisone or equivalent). When symptoms improve to Grade 1 or

less, corticosteroid taper should be started and continued over at least 1 month. Guidelines for continuing treatment with pembrolizumab can be found in Appendix 5.

All patients who experience diarrhoea should be advised to drink liberal quantities of clear fluids. If sufficient oral fluid intake is not feasible, fluid and electrolytes should be substituted via IV infusion.

6.5.1.2 Nausea/vomiting:

Nausea and vomiting should be treated aggressively, and consideration should be given in subsequent cycles to the administration of prophylactic antiemetic therapy according to standard institutional practice. Patients should be strongly encouraged to maintain liberal oral fluid intake.

6.5.1.3 Anti-infectives:

Patients with a documented infectious complication should receive oral or IV antibiotics or other anti-infective agents as considered appropriate by the treating investigator for a given infectious condition, according to standard institutional practice.

6.5.1.4 Immune-related adverse events:

Please see Section 6.6 below regarding diagnosis and management of adverse experiences of a potential immunologic etiology.

6.5.1.5 Management of Infusion Reactions:

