12.1.3 Criteria for Retreatment

Following the first dose of cisplatin and the first dose of MK-3475, 2 further doses of cisplatin or carboplatin and 6 additional doses of MK-3475 will be given. Cisplatin or carboplatin will be given concurrently with radiation to a total of 70 Gy. These subsequent doses are at the discretion of the investigator and consent from the patient. If the patient meets any of the following criteria, treatment will be delayed 1 week and the patient will be re-evaluated.

- Neutrophils $\leq 1,500/\text{mm}^3$
- Platelets $\leq 75,000/\text{mm}^3$
- Grade 3 - 4 hematologic toxicities

- Grade 3 - 4 non-hematologic toxicities

Initiation of cisplatin or carboplatin re-treatment may be delayed for a maximum of 14 days to allow recovery from any toxicity. If the toxicity has not resolved within 14 days of the planned treatment date, re-treatment may occur if the patient is responding to treatment and there is agreement with the Trial Steering Committee.

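### Platinum and pembrolizumab instructions conflict in three places: the neutrophil threshold for re-treatment, Grade 3 enterocolitis, and the carboplatin base dose in 6.2.1

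*Combined protocol and SAP*

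**What the plan says.** **Neutrophils.** Section 12.1.1.1 withholds cisplatin when the count is below 1,200/mm³ and adds "When toxicity resolves (ANC > 1200) reinitiate cisplatin at same dose". Section 12.1.2 gives carboplatin at 50% for counts of 1,000 to 1,999 and holds it for a week below 1,000. Section 12.1.3 covers the two further platinum doses and six further MK-3475 doses. It lists neutrophils of 1,500/mm³ or less among its criteria and says: "If the patient meets any of the following criteria, treatment will be delayed 1 week and the patient will be re-evaluated". It refers to neither table.

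**Grade 3 enterocolitis.** Section 6.5.1.1 has an entry beginning "In patients with severe enterocolitis (Grade 3", under which pembrolizumab is to be "permanently discontinued". Table 10 (section 6.3.9.2) holds it for Grade 2-3 diarrhoea or colitis and allows restart at Grade 0-1. Section 6.6 and Appendix 5 withhold at Grade 3 and discontinue at Grade 4.

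**Carboplatin.** Section 6.2.1 states one dose, 100 mg/m² with in-patient hydration, for cisplatin or carboplatin alike. Sections 3.2, 6.3.7, 12.1.1.2, 12.1.1.3 and 12.1.1.5 give carboplatin at AUC 5, and 6.3.7 allows it as an outpatient.

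**The concern.** Each item gives two different instructions for the same patient on the same day, and the protocol does not say which one prevails.

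The first decides whether a platinum dose in curative-intent treatment is given on time or a week late. Section 1.2.2 treats that as important: "In such patients, any interruptions or delays to chemoradiotherapy can have a negative impact on treatment outcomes". The second decides whether a patient who has recovered from Grade 3 enterocolitis may ever receive pembrolizumab again. The third sits in the section headed as the chemotherapy dose, which is where a prescriber would look, and would underdose carboplatin if taken at its word.

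What is at stake is patient safety and uniform treatment across the cohorts, rather than the statistical design.

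**Working it through.** **Neutrophils.** The three rules applied to the same count at a re-treatment visit:

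| Count (/mm³) | Cisplatin, 12.1.1.1 | Carboplatin, 12.1.2 | Section 12.1.3 |
|---|---|---|---|
| below 1,000 | withhold | hold 1 week | delay 1 week |
| 1,000-1,199 | withhold | 50% | delay 1 week |
| 1,200 exactly | not covered | 50% | delay 1 week |
| 1,201-1,500 | same dose | 50% | delay 1 week |
| 1,501-1,999 | same dose | 50% | no delay |

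The cisplatin conflict spans 1,500 − 1,200 = 300 cells/mm³ and the carboplatin conflict 1,500 − 1,000 = 500. Both arise at the two re-treatment doses, days 22 and 43. Reinitiating cisplatin can only happen after dose 1, so 12.1.1.1 and 12.1.3 govern the same doses. If 1,500 always prevailed, the 1,200 restart would never operate.

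**Timing of dose 3.** A one-week delay moves it to day 43 + 7 = 50. Thirty-five uninterrupted weekday fractions from day 1 end on day 47 (Monday start) or day 49 (any other weekday). Table 2, however, labels cycle 1 as week 0, so week 7 is day 7 × 7 + 1 = 50, and radiotherapy is still listed there: "C3 Wk 7 is not a clinic visit. Patient will continue to receive radiotherapy only".

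**Grade 3 enterocolitis.** The four places concern the same event. Table 13 (section 7.6.1) lists enterocolitis under colitis as an event of clinical interest, and sections 6.3.9.2 and 6.6 send such events to Appendix 5. One place discontinues and three withhold, of which only Table 10 expressly permits restart after Grade 3. Steroid instructions also differ. At Grade 2, 6.5.1.1 gives an example of 0.5 mg/kg/day prednisone once symptoms have lasted more than a week, against 1-2 mg/kg/day in Appendix 5. At Grade 3 both give prednisone 1-2 mg/kg/day, but Appendix 5 starts with methylprednisolone 125 mg IV.

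**Carboplatin.** Section 12.1.1.2 gives the AUC 5 dose as 5 × (GFR + 25) mg. The documents give no distribution of BSA or GFR, so both ranges are assumptions.

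- Literal dose: 100 × 1.6 = 160 mg to 100 × 2.0 = 200 mg.
- AUC 5 at GFR 50: 5 × 75 = 375 mg; at GFR 120: 5 × 145 = 725 mg.
- Ratio: 160/725 = 22% to 200/375 = 53%.
- For patients switched for renal function (GFR 30-50 under 12.1.1.3), AUC 5 is 275-375 mg, and the ratio is 160/375 = 43% to 200/275 = 73%.

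These ranges pair the smallest BSA with the highest GFR and the reverse, so they are outer bounds within the assumptions.

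**The case against.** The best defence on neutrophils is that 12.1.3 is a stricter gate laid over the tables. For carboplatin that works in part: delay at 1,500 or below, then 50% at 1,501-1,999. Section 12.1.3 also leaves later doses to the investigator's discretion. But the text does not call it an overriding gate, its delay sentence is mandatory, and for cisplatin the reading makes the 1,200 restart redundant. The gap is real, though one precedence sentence could close it.

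A reader might infer that the conflict takes dose 3 out of concurrent treatment, since 12.1.3 says: "Cisplatin or carboplatin will be given concurrently with radiation to a total of 70 Gy". The documents do not support that. On an uninterrupted weekday course day 50 falls after the last fraction, but Table 2 still shows radiotherapy at week 7. Any one-week hold of dose 3 has the same effect, including an undisputed hold below 1,200, and 12.1.3 itself allows delays of up to 14 days.

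A reader might also infer from the three-to-one count that withholding is the intended rule at Grade 3. The count makes 6.5.1.1 the outlier but does not show intent. Section 1.2.2 stresses caution with an untested combination, and aligning to the majority relaxes a safety rule.

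On carboplatin, the objection that this is a slip in a base-dose statement, and not a dose-modification rule, is correct. Section 6.3.7 uses the same hydration wording for cisplatin alone, and 6.2.1 points to Appendix 1, where AUC 5 appears.

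**Conclusion.** All three contradictions stand in the current text, and nothing elsewhere resolves them. The two dose-modification conflicts cover neutrophils above 1,200 and up to 1,500 for cisplatin, 1,000 to 1,500 for carboplatin, and pembrolizumab after Grade 3 enterocolitis. The third is a probable drafting slip that, followed literally, would give roughly 20-55% of the AUC 5 dose under the main BSA and GFR assumptions. The documents give no event rates, so no frequency is claimed.

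It would go too far to conclude that the primary endpoint is compromised. A toxicity-related delay of more than two weeks is a DLT, so the neutrophil threshold could in principle affect how long a hold lasts. But a one-week delay, or even 14 days, does not by itself meet that criterion, and the documents give no basis for estimating any shift in DLT counts. The corrections should be made, as patient-safety wording.

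**What to change.** 1. In 12.1.3, first state which treatment the criteria delay: platinum, MK-3475 or both. This must come first, because simply deleting the neutrophil line could remove a gate meant for MK-3475; section 6.3.9.2 otherwise holds pembrolizumab for haematological toxicity only at drug-related Grade 4. Then set one neutrophil threshold for platinum re-treatment. Either refer platinum to 12.1.1.1 and 12.1.2 and keep any intended MK-3475 gate, or change both tables to 1,500.
2. For Grade 3 enterocolitis, the sponsor confirms the intended rule and makes 6.5.1.1, Table 10, section 6.6 and Appendix 5 agree. The default is to align 6.5.1.1 with Table 10 and Appendix 5, steroid treatment included. If permanent discontinuation is intended, the other three places change instead.
3. Amend 6.2.1 to read: cisplatin 100 mg/m² with in-patient pre- and post-hydration, or carboplatin AUC 5.

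The cost is amendment wording in 6.2.1, 12.1.3 and 6.5.1.1, or in the corresponding tables and sections if the sponsor chooses the other option. Visits, sample size, DLT definition and analyses stay as they are.
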